## Exclusion Criteria:

Subjects who meet any of the following criteria will be excluded from study participation:

- 1. Patient weighing < 13kg
- 2. Allergy to porcine products
- 3. Previous sensitization or allergy to trypsin, pancreatin, or pancrelipase
- 4. History of severe head trauma, as defined by loss of consciousness or hospitalization, skull fracture or stroke.
- 5. Seizure within the last year prior to enrollment, or the use of seizure medications either at present or in the past.
- 6. Diagnosed with any of the following:
  - a. HIV-positive
  - b. Cancer (regardless of remission state)
  - c. Cerebral palsy
  - d. Muscular dystrophy
  - e. Known genetic disorder or abnormality
  - f. Blood dyscrasia
  - g. Ongoing gastrointestinal disease (e.g., Crohn's Disease, Celiac Disease. Not intended to exclude gastrointestinal issues, such as constipation or diarrhea not associated with another GI disease diagnosis.)
  - h. Endocrine disorder (e.g., hypothyroidism, diabetes)
  - i. Pancreatic disease (endocrine or exocrine)
  - j. Previous diagnosis with or hospitalization for significant co-morbid psychiatric conditions such as depression, bipolar or other psychiatric disease (Not intended to exclude ADHD, anxiety associated with autism or obsessive-compulsive disorder)
  - k. Any diagnosis of sleep or wakefulness disorder, such as narcolepsy, hypo or hypersomnia.
- 7. Evidence or history of severe, moderate or uncontrolled systemic disease, or history of metabolic disorders (e.g., amino acid deficiencies, hypoketosis)
- 8. Any co-morbid condition which in the Investigator's or Medical Director's opinion makes it undesirable for the subject to participate in the trial or would jeopardize compliance with the protocol.
- 9. Supplementation with any of the following within 30 days of entering the study:
  - a. Any enzyme product or a product containing pancreatic/digestive enzymes of plant or animal origin
  - b. Pancreatin, thyroid, or adrenal extracts, either synthetic, plant or animal-based
  - c. Essential fatty acids, omegas, or other supplement containing these products (does not require a washout)
  - d. Amino acids, or amino acid containing products
  - e. Any secretin product including transdermal, oral, or injectable
  - f. Vitamin B12/folate either oral or injectable (Allowable as part of a multivitamin. Folate not to exceed 400 mcg, B12 not to exceed 12 mcg). No injectables allowed of either.

	g. Chelating agents / chelation therapy
	h. Any other investigational drug or therapy, oncology drug, anti- helminthic, or anti-yeast drug
	i. Off-label medications
	10. Asthma, when medication (oral, inhaled, or injectable) is given on a daily basis or is necessary >3 times per week.
	11. Ongoing dietary restriction for allergy or other reasons except nut allergies (lactose-free allowable)
	12. Inability to ingest the study drug
	13. Inability to follow the prescribed dosing schedule
	14. Subjects who are likely to experience significant changes in their ongoing psychosocial or medical treatments for autism over the course of the trial (e.g., initiation of new behavioral therapy, initiation of new medication or alternative treatment). Minor changes in ongoing treatment (e.g., missed therapy sessions due to holiday/vacation; planned break in therapy due to school holidays) will not be considered significant.
	15. Use of any stimulant medication or other medication given for ADHD must be discontinued 5 days prior to entering the study (Vayarin requires a 30-day washout)
	16. Subjects taking an SSRI must be on a stable dose for a minimum of 30 days prior to entering the study.
	17. History of premature birth < 35 weeks gestation
	18. Prior history of stroke in utero, or other intrauterine insult
Additional Inclusion Criteria at Visit 1/Baseline for	The subject must meet the following additional inclusion criteria upon returning for Visit 1/Baseline in order to be randomized:
Randomization:	
 
The subject must have demonstrated IP compliance that is ≥50% during the 2-week blinded drug run-in period
 
Upon retest at Visit 1/Baseline, the subject's score on the ABC-I must have increased or decreased by less than 30%, and also must be ≥9
 
Subjects must continue to meet all inclusion/exclusion criteria
 

## Statistical Considerations:

The sample size is based on (a) the primary efficacy variable of the change from baseline to week 12 for the Aberrant Behavior Checklist (ABC) subscale for Irritability; (b) the primary analysis set of low-level fecal chymotrypsin (FCT)  $\leq$  12.6 Units/gram randomized subjects; and (c) a 1:1 randomization scheme. Assuming a mean  $\pm$  standard deviation decrease in ABC Irritability from baseline to week 12 of  $3.7 \pm 7$  for CM-AT and  $0.6 \pm 5$  for Placebo, a sample size of 82 evaluable low-level subjects per treatment group yields 90% power to declare a statistically significant difference between treatments at a two-sided 0.05 level of significance. Assuming 15% premature withdrawal, 97 low-level subjects will be randomized. In order to achieve 97 randomized low-level subjects per group, a total of 162 subjects per group will be randomized (based on previous data indicating 60% of autistic children are low-level).

Primary analyses (assessing CM-AT vs. Placebo difference) on change from baseline to week 12 will be estimated from a Mixed Model Repeated Measures (MMRM) across all visits assuming the unstructured within-subject correlation structure. Included in the model will be the main effects of randomized treatment group, visit, baseline ABC irritability, study center and the treatment-by-visit interaction effect. Analyses with and without imputation for missing data will be performed.

If statistical significance, in favor of CM-AT, is shown on the primary efficacy endpoint in the primary analysis set of low-level randomized patients (FCT  $\leq$  12.6 Units/gram), the study will be considered to be a success statistically. The secondary efficacy variable is change from baseline to week 12 in ABC Lethargy/ Social Withdrawal (ABC-L) of low-level randomized patients (FCT  $\leq$  12.6 Units/gram).

As an exploratory analysis, the MMRM analyses will be repeated on the ABC-I and ABC-L for the non-low-level FCT randomized patients (FCT > 12.6 Units/gram)

As an additional exploratory analysis, the above MMRM analyses will be repeated on the ABC-I and ABC-L on all randomized patients in a similar manner as for the low-level randomized patients.

For safety, fecal globin levels, the presence of occult blood,  $\alpha_1$ -antitrypsin, and weight loss will be used to monitor the safety and tolerability of CM-AT. These safety measures will be presented descriptively by treatment group. No formal statistical comparisons will be carried out.

STATISTICAL ANALYSIS PLAN Protocol ID:00103 / Autism

A Double Blind Randomized Placebo Controlled Study of CM-AT for the Treatment of Autism in Children With All Levels of Fecal Chymotrypsin

Document Date: 27 December 2017

Upload Date: 2 May 2021

STATISTICAL ANALYSIS PLAN Amendment 1

A Double Blind Randomized Placebo Controlled Study of CM-AT for the Treatment of Autism in Children with All Levels of Fecal Chymotrypsin

PROTOCOL No. 00103 Autism

Sponsor:

Curemark, LLC

Date:

December 27, 2017

Approvals (sign and date):

Curemark, LI

[name], Ch

[name], Statistician

TABLE OF CONTENTS

1.	Study Objectives	3
2.	Study Design	3
	Study Analysis Sets	
4.	Test product, Dose and Mode of Administration	6
5.	Demographics, Other Baseline Characteristics (other than efficacy and safety	
	variables), Study Drug Compliance	6
6.	Efficacy Variables	7
7.	Safety Parameters	9
8.	Statistical Methodology	10
9.	Interim Efficacy Analysis	18
10	. Software	19
Sc	oring of the Aberrant Behavior Checklist (ABC)	20

1. Study Objectives

To examine children with autism at all levels of fecal chymotrypsin using the Aberrant Behavior Checklist.

Endpoint (outcome) measurements to determine efficacy of treatment with CM-AT versus placebo for changes in the Aberrant Behavior Checklist subscale for Irritability/Agitation (ABC-I) between Baseline (defined as score at Screening Part 1 for efficacy assessments; in the event a subject has more than one Screening Part 1 value, the value to be used will be the last value of the variable measured prior to start of randomized treatment) and Week 12 visit and changes in the Aberrant Behavior Checklist subscale for Lethargy/Social Withdrawal (ABC-L) between Baseline and Week 12 of treatment.

To continue to monitor the safety of CM-AT in this population of children.

2. Study Design

This is a Phase III, multi-center, randomized, double-blind, placebo-controlled study of approximately 300 subjects diagnosed with autism from approximately 35 clinical sites in the United States. Subjects will be between 3 and 8 years of age (inclusive) at the time of consent. All study participants must have an initial ABC-I score ≥ 11 and a diagnosis of Autistic Disorder as demonstrated by the Diagnostic and Statistical Manual for Mental Disorders IV Text Revision (DSM-IV-TR) and by the Autistic Diagnostic Interview − Revised (ADI-R). Subjects will also be screened using the Social Communication Questionnaire (SCQ) and must achieve a score ≥ 15 to be considered eligible.

After initial screening criteria are met, including the diagnosis of Autistic Disorder as demonstrated on the DSM-IV-TR, SCQ and ADI-R, the study participants will be administered the ABC. If their ABC-I score is greater than or equal to $11 (\geq 11)$ they can be enrolled and given a two-week initial blinded placebo run-in. At the end of the run-in, subjects will be evaluated and randomized if all inclusion criteria are satisfied.

The compliance and inclusion criteria required for randomization are: 1) subjects must take the study drug on the prescribed regimen and 2) continue to meet inclusion criteria. At the Visit 1 Visit, they will be reevaluated for their level of Irritability/Agitation with the ABC-I scale. If a subject's score on the ABC-I scale has increased or decreased by 30% or more, or is <9 on the retest, they will be discontinued from the study and not randomized. Qualified subjects can be randomized into the study if they meet all inclusion/exclusion criteria.

After enrolling in the study at a clinical site, subjects ultimately randomized to treatment will receive study drug or placebo three times daily with food for a

period of 12 weeks. Parents will keep a missed dose log. Subjects will be seen at Week 2, 4, 6, 8, 10, and 12, post-randomization. Standardized measures of behavior, health, and quality of life will be utilized. In addition, measures of overall health including growth and weight will be obtained.

Subjects will be randomized in a 1:1 ratio to CM-AT or Placebo (both biomarker negative (>12.6 U/g) and positive (≤12.6 U/g) will be included). Randomization will be based upon study drug vs placebo.

Subjects will be randomized to ensure 82 subjects per study arm of the low-level fecal chymotrypsin (FCT) children are evaluable for the primary statistical analysis (treatment comparison on the primary endpoint of change in ABC irritability from Baseline to Week 12 on the primary analysis set of children with FCT \leq 12.6 in randomized subjects). The FCT value used in determination of whether the patient has FCT \leq 12.6 is the Screening Part 1 value; if the patient has more than one screening FCT, the last FCT measured prior to randomization will be used to determine whether the patient has FCT \leq 12.6. It is anticipated that each site will enroll approximately 3 to 5 subjects per month and the study will be open for a period of twelve months. A power recalculation may be performed midway through Study Protocol 00103 to determine if sufficient numbers of biomarker negative children have been enrolled.

A subject may enroll in Study Protocol 00104 Open Label Extension after successfully completing Week 12 of Study Protocol 00103. The analyses of data collected in Study Protocol 00104 Open Label Extension will be discussed in a separate analysis plan.

3. Study Analysis Sets

One-hundred sixty-two (162) subjects will be randomized per treatment arm, or 324 subjects total. These subjects will be randomized from approximately 35 sites throughout the United States. Approximately 350 subjects will be enrolled into the placebo run-in period to ensure that 324 will be randomized. At the completion of the two-week placebo run-in, the subject will be assessed for compliance and ABC-I scores. If a subject's score on the ABC-I scale has increased or decreased by 30% or more, or is <9 on the retest, they will be discontinued from the study and not randomized.

The study population will consist of children, both males and females, between 3 and 8 years of age inclusively at the time of consent. All study participants must have an initial ABC-I score of ≥ 11 and a diagnosis of Autistic Disorder as demonstrated by the DSM-IV-TR and by the ADI-R. Subjects will also be screened using the SCQ and must achieve a score of ≥ 15 to be considered eligible.

The following populations form the basis of the analysis sets that will be included in efficacy and safety analyses (not listed in order of analysis below. For order of analysis see Section 6.0):

Intent-to-Treat (ITT): All randomized subjects who received study drug and had at least one post-Baseline ABC-I assessment.

Low-level FCT ITT: All randomized subjects with pathologically low levels of FCT (≤12.6 U/g) who received study drug and had at least one post-Baseline ABC-I assessment. Subjects are analyzed under the treatment to which they are randomized. This is the primary analysis population for efficacy.

Non-Low-Level FCT (FCT >12.6) ITT: All non-low-level (FCT >12.6 U/g) randomized subjects who received study drug and had at least one post-Baseline ABC-I assessment. Subjects are analyzed under the treatment to which they are randomized. This is an exploratory analysis population for efficacy.

All Randomized: All randomized subjects. This is an exploratory analysis population for efficacy. Subjects are analyzed under the treatment to which they are randomized.

Low-level FCT All Randomized Subjects: All randomized subjects with pathologically low levels of FCT (≤12.6 U/g). This is a population for use in a sensitivity analysis of efficacy. Subjects are analyzed under the treatment to which they are randomized.

Non-Low-Level FCT (FCT >12.6) All Randomized Subjects: All non-low-level (FCT >12.6 U/g) randomized subjects. Subjects are analyzed under the treatment to which they are randomized. This is an exploratory analysis population for efficacy.

Per-Protocol (PP): All ITT subjects who have completed a Week 12 visit and have a Week 12 ABC-I score. Subjects are analyzed under the treatment to which they are randomized. This is an exploratory analysis population for efficacy.

Low-Level FCT (FCT \leq 12.6) Per Protocol (PP): All low-level (FCT \leq 12.6 U/g) PP Subjects. Subjects are analyzed under the treatment to which they are randomized. This is an exploratory analysis population for efficacy.

Non-Low-Level FCT (FCT >12.6) PP: All non-low-level (FCT >12.6 U/g) PP Subjects. Subjects are analyzed under the treatment to which they are randomized. This is an exploratory analysis population for efficacy.

Run-in Analysis Set: All subjects receiving at least one dose of placebo during the placebo-run in phase. All subjects will be analyzed as one group.

Safety Analysis Set: All subjects receiving at least one dose of randomized treatment. Subjects are analyzed under the treatment received. This is a primary analysis set for safety.

Low-Level FCT (FCT \leq 12.6) Safety Analysis Set: All Low-Level subjects (FCT \leq 12.6) receiving at least one dose of randomized treatment. Subjects are analyzed under the treatment received. This is the secondary analysis set for safety.

4. Test product, Dose and Mode of Administration

900mg of CM-AT (pancreatic enzyme concentrate encapsulated in hydrogenated soybean oil) 3x daily sprinkled over food. To be taken with a meal or large snack.

5. Demographics, Other Baseline Characteristics (other than efficacy and safety variables), Study Drug Compliance

"Baseline" for variables other than efficacy and safety refers to the last value of the variable measured prior to start of randomized treatment. For efficacy and safety, "Baseline" is defined as the value measured at Screening Part 1, denoted as "Screening" below.

- 5.1 Demographics Baseline demographics of age, gender (male; female), ethnicity (Hispanic or Latino; not Hispanic or Latino), race (American Indian or Alaska Native; Asian; Black or African American; Native Hawaiian or other Pacific Islander); height (cm), weight (kg), body mass index (BMI).
- 5.2 Physical examination abnormalities by body system (HEENT, Respiratory, Cardiovascular, Abdomen, Musculoskeletal, Central Nervous System, Dermatologic, General Appearance, Other)
- 5.3 Responses to each question on Study Specific Medical History questionnaire
- 5.4 Response to each question on Neurodevelopmental history questionnaire
- 5.5 Responses to each question on Family History questionnaire
- 5.6 Responses to each question on Parent Visit questionnaire
- 5.7 Screening ABC-I score. The scoring of this subscale is given in Appendix A.
- 5.8 Screening DSM-IV-TR total score and sub-scores (Social Interaction; Communication; Behavior) as described in Appendix C.

- 5.9 Screening SCQ total score and sub-scores (Social Interaction; Communication; Restricted, Repetitive, and Stereotyped Patterns of Behavior).
 - The total score and the subscales of Reciprocal Social Interaction, Communication, and Restricted, Repetitive, and Stereotyped Patterns of Behavior domain are given in Appendix B.
- 5.10 Screening ADI-R (Total A, Verbal Total B, Nonverbal Total B, Total C and Total D). These scores are determined by the rater and recorded directly on the questionnaire.
- 5.11 Study Drug compliance will be assessed based upon the sachet usage. The calculation for percentage of compliance is 100 times the number of sachets dispensed at the previous visit minus the number of sachets returned, divided by the days between visits times 3 (not including days after the last visit at which sachets were dispensed if the subject did not return after that last visit). Study drug compliance during the 2-week placebo run-in period and during the randomized double-blind treatment period will be analyzed.

6. Efficacy Variables

The following lists the efficacy variables that will be collected on each subject and analyzed. Section 7 of this document provides the details of the analysis methodology.

- 6.1 **The primary efficacy variable** is the change from Baseline (score at Screening Part 1) to Week 12 in the Aberrant Behavior Checklist (ABC) subscale for Irritability/Agitation (ABC-I) in Low-level FCT ITT subjects. The subscale item components are given in Appendix A. Only the raw scores will be analyzed.
- 6.2 The **secondary efficacy variable** is the change from Baseline (score at Screening Part 1) to Week 12 for the Aberrant Behavior Checklist subscale for Lethargy/Social Withdrawal (ABC-L) in Low-level FCT ITT subjects. The scoring of this subscale is given in Appendix A. Only the raw scores will be analyzed.
- 6.3 Exploratory Efficacy Variables include:
 - Behavioral changes from Baseline (score at Screening Part 1 unless otherwise specified) to Week 12 (the scoring of these subscales is given in Appendix A):

Aberrant Behavior Checklist							
	FCT ≤12.6 U/g	FCT >12.6 U/g	FCT – All Levels				
ABC Irritability		X	X				
ABC Lethargy		X	X				
ABC Hyperactivity	X	X	X				
ABC Stereotypy	X	X	X				
ABC Inappropriate Speech	X	X	X				
ABC Total Score	X	X	X				
Additional Exploratory Endpoints							
Clinical Global Impression – Improvement	X	X	X				
Clinical Global Impression – Severity (Baseline is the value measured at the randomization visit)	X	X	X				
Social Responsiveness Scale ((Baseline is the value measured at the randomization visit)	X	X	X				
Pediatric Quality of Inventory							
Physical Functioning	X	X	X				
Emotional Functioning	X	X	X				
Social Functioning	X	X	X				
Cognitive Functioning	X	X	X				
Communication	X	X	X				
Worry	X	X	X				
Daily Activities	X	X	X				
Total Score	X	X	X				

- Gastrointestinal measures will be performed at each regularly scheduled visit, with abnormality status assessed at each visit and with change defined as the difference between Baseline (measures from Screening Part 1) to Week 12.
- Weight will be assessed at each regularly scheduled visit,
- Weight gain is defined as Post-Baseline weight ≥ Baseline weight (Baseline weight is the weight at Screening Part 1. If a patient has more than one Screening Part 1 weight, the last weight measured prior to randomization will be used).
- Weight loss is defined as Post-Baseline weight ≤ Baseline weight.

Stool Test Panel & Weight Change						
	FCT ≤12.6 U/g	FCT >12.6 U/g	FCT – All Levels			
C.Diff. Tox A&B	X	X	X			
A1-Antitrypsin	X	X	X			
Fecal Chymotrypsin	X	X	X			
Cryptosporidum AG	X	X	X			
H Pylori Ag,	X	X	X			
pH Stool	X	X	X			
Weight	X	X	X			

7. Safety Parameters

- 7.1 Adverse Events Incidence of treatment emergent adverse events are collected for each subject. A run-in emergent adverse event is defined as an event starting or worsening after the start of placebo run-in phase and before the start of double-blind treatment. A treatment emergent adverse event (TEAE) is defined as an event starting or worsening on or after the start of double-blind treatment. Each adverse event will be coded to a MedDRA system organ class (SOC) and preferred term (PT). Severity, seriousness and relationship to study drug for each event will also be collected.
- 7.2 A complete physical exam is conducted at the start of the placebo run-in phase. Brief physical exams are conducted at the randomization visit (prior to randomization) and during the double-blind phase. If clinically significant findings are identified during the physical exam, an adverse event form will be completed.
- 7.3 Stool pH is collected at Baseline (Screening Part 1) and at several Post-Baseline visits including Week 12. The value at each visit and the change from Baseline at each Post-Baseline visit will be analyzed.
- 7.4 For each subject at each visit at which Stool pH is collected, the incidence of abnormal outcomes for stool pH (<5.92 or >8.00), fecal globin (present) and fecal occult blood (present) are collected.
- 7.5 A1-Antitrypsin in the feces from the Fecal Panel is collected at Baseline (Screening Part 1) and Post-Baseline. It will be the variable for analysis along with the change from Baseline at each Post-Baseline visit. Additionally, at each time point for which α1-antitrypsin is measured, each subject's incidence of A1-Antitrypsin <55 and ≥55 will be recorded.

7.6 Vital signs - The analysis variables are the change from Baseline (Screening Part 1) at each Post-Baseline at each visit for visit for weight (kg), systolic blood pressure (mmHg), diastolic blood pressure (mmHg) and pulse (beats per minute).

8. Statistical Methodology

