	Other measures: DSM-IV, SCQ and ADI-R.
Study Objectives:	Endpoint (outcome) measurements for treatment with CM-AT versus placebo in biomarker negative and positive subjects will be analyzed as described in Statistical Considerations.
	PRIMARY ENDPOINT MEASUREMENTS
	• Aberrant Behavior Checklist: subscale of Irritability/Agitation (ABC-I) at FCT levels ≤ 12.6
	SECONDARY ENDPOINT MEASUREMENTS
	
 
Aberrant Behavior Checklist: subscale of Lethargy/Social Withdrawal (ABC-L) at FCT levels ≤ 12.6
 

	EXPLORATORY ENDPOINT MEASUREMENTS
	Behavioral changes:
	(ABC-I) at FCT levels > 12.6
	
 
Aberrant Behavior Checklist: subscale of Lethargy/Social Withdrawal (ABC-L) at FCT levels > 12.6
 

	o Aberrant Behavior Checklist: subscale of Hyperactivity (ABC-H)
	at FCT levels ≤ 12.6  O Aberrant Behavior Checklist: subscale of Total (ABC-T) at FCT levels ≤ 12.6

	
 
Aberrant Behavior Checklist: subscale of Stereotypy (ABC-S) at FCT levels ≤ 12.6
 
Aberrant Behavior Checklist: subscale of Inappropriate Speech
 

	(ABC-IS) at FCT levels ≤ 12.6  ○ Aberrant Behavior Checklist: subscale of Irritability/Agitation
	
 
(ABC-I) at all FCT levels
 
Aberrant Behavior Checklist: subscale of Lethargy/Social
 
Withdrawal (ABC-L) at all FCT levels
 

	
 
Aberrant Behavior Checklist: subscale of Hyperactivity (ABC-H) at all FCT levels
 

	
 
Aberrant Behavior Checklist: subscale of Total (ABC-T) at all FCT levels
 

	
 
Aberrant Behavior Checklist: subscale of Stereotypy (ABC-S) at all FCT levels
 

	
 
Aberrant Behavior Checklist: subscale of Inappropriate Speech (ABC-IS) at all FCT levels
 

	

Pediatric Quality of Life Inventory (PedsQL)

CGI-I, CGI-S

	o SRS-2
	GI health:     Stool Test Panel
	Weight gain/loss
	SAFETY ENDPOINT MEASUREMENTS
	
 
Adverse Events
 
Negative change in weight, if clinically inappropriate based upon standard scales
 

	
 
Incidence and/or change in clinical laboratory results for the following:
 
Fecal globin / Fecal occult blood
 

	
 
Stool pH
 
Presence or continued growth of pathogens, as indicated by stool panel antigen/toxin tests
 
Elevated α1-antitrypsin levels
 
Change in bowel habits due to colitis
 

Inclusion Criteria:	1. Age between 3 and 8 years, inclusive at the time of consent

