For continuous exploratory endpoints, treatments will be compared on change from Baseline in a similar manner as the primary endpoint at Week 12 and each Post-Baseline visit except for multiple imputation and assessment of treatment-by-study center interaction effects. For CGI-S, an endpoint for which there is no Baseline value, treatments will be compared in a similar manner as the primary endpoint on the CGI-S value itself (as opposed to a change from Baseline) without a Baseline value of the endpoint as a covariate. There will be no adjustment for multiple comparisons.

For dichotomous exploratory endpoints (stool test, weight gain/loss), no formal statistical hypothesis testing will be performed to compare the treatment groups on these results.

The number and percentage of subjects experiencing the dichotomous endpoint will be presented for each treatment group. For completeness, this analysis will be repeated for each visit.

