Fecal Panel - For Fecal Chymotrypsin, pH and A1-Antitrypsin, descriptive statistics (number of subjects, mean, median, standard deviation, minimum and maximum) of Baseline (Screening Part I), each Post-Baseline visit and the change from Baseline at each Post-Baseline visit will be presented. Treatment groups will be compared on change from baseline at each visit using analysis of covariance adjusting for study center and Baseline. For Fecal Chymotrypsin, the number and percentage of subjects with values >12.6 U/g and \le 12.6 U/g at each visit will be presented. For pH, the incidence rate (number and percentage of subjects) with abnormal outcomes will be presented at each visit. For A1-Antitrypsin, the number and percentage of subjects with values <55 and ≥55 will be presented at each visit. Further, for fecal globin and fecal occult blood the incidence rate (number and percentage of subjects) with abnormal outcomes will be presented at each visit, where abnormal is defined as the variable being "present". No formal statistical hypothesis testing will be performed to compare the treatment groups on these results.

Vital signs – For each of the following measurements: weight (kg), systolic blood pressure (mmHg), diastolic blood pressure (mmHg) and pulse (beats per minute), descriptive statistics (number of subjects, mean, median, standard deviation, minimum and maximum) of Baseline, each Post-Baseline visit and the change from Baseline at each Post-Baseline visit will be presented. No formal statistical hypothesis testing will be performed to compare the treatment groups on these results.

Weight Loss by End of Study - The number and percentage of subjects losing weight by the end of the study will be tabulated for each visit for each treatment group. No formal statistical hypothesis testing will be performed

to compare the treatment groups on the proportion of subjects with weight loss.

9. Interim Efficacy Analysis

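### SAP 6.3 puts equality in both the weight-gain and the weight-loss rule, so a child with unchanged weight is counted as both

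*SAP*

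**What the plan says.** The two definitions are adjacent bullets in SAP Section 6.3, Exploratory Efficacy Variables: "Weight gain is defined as Post-Baseline weight ≥ Baseline weight" and "Weight loss is defined as Post-Baseline weight ≤ Baseline weight". The reference value is fixed in the first of them: "Baseline weight is the weight at Screening Part 1", or the last such weight before randomization if there is more than one. No category for unchanged weight is given.

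The categories are used in Section 8.6.3: "For dichotomous exploratory endpoints (stool test, weight gain/loss), no formal statistical hypothesis testing will be performed". That section instead presents the number and percentage in each treatment group, repeated at each visit.

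Section 8.7 has a separate safety output on weight loss: "The number and percentage of subjects losing weight by the end of the study will be tabulated for each visit for each treatment group". It neither defines losing weight nor refers back to 6.3. Weight is also analysed as a continuous safety variable. Section 7.6, which covers weight with the other vital signs, says "The analysis variables are the change from Baseline (Screening Part 1) at each Post-Baseline at each visit".

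The protocol's Statistical Considerations name weight among the tolerability markers: "weight loss will be used to monitor the safety and tolerability of CM-AT". The synopsis words the safety endpoint as "Negative change in weight, if clinically inappropriate based upon standard scales".

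**The concern.** A gain/loss split should place each child in one category only. These two rules overlap at exactly one point, no change, and an unchanged reading is possible whenever weights are recorded on a rounded scale. This is a stated rule that gives a wrong count if programmed literally, not a detail left open.

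The SAP separates categories cleanly elsewhere. Sections 7.5 and 8.7 split A1-antitrypsin at below 55 versus 55 or above, and Section 8.7 splits fecal chymotrypsin at above 12.6 versus 12.6 or below. The weight rule departs from that practice.

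At stake is the accuracy of descriptive percentages on a marker that the protocol links to possible malabsorption. No test is planned on these tables, so the percentages are the whole result. The error runs both ways: it overstates loss, the unfavourable outcome, and gain, the favourable one, by the same amount.

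**Working it through.** **1. What follows from the definitions alone.** Let B be the Baseline weight and X the post-Baseline weight, both as recorded. The plan states no expected weight-loss rate, so there is no figure to reproduce.

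- Loss as defined: P(X ≤ B) = P(X < B) + P(X = B)
- Gain as defined: P(X ≥ B) = P(X > B) + P(X = B)
- Sum: 100% + P(X = B)

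Each rate is therefore too high by exactly the unchanged share. The error cannot be negative, and it is zero only if no weight is unchanged. As an illustration (assumed figures), take 15% lost, 10% unchanged and 75% gained. The SAP rules report loss 15 + 10 = 25% and gain 75 + 10 = 85%, which sum to 110%. With 15% true loss and 5% or 20% unchanged, reported loss is 20% or 35%.

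**2. Plausible size at Week 12.** The documents give no weighing precision, growth rate or SD, so these are assumptions: readings to 0.1 kg, and change normal with mean +0.55 kg and SD s. To a close approximation an unchanged reading is a change between −0.05 and +0.05 kg, so

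- strict loss = Φ((−0.05 − 0.55)/s)
- loss under the SAP rule = Φ((0.05 − 0.55)/s)

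| s (kg) | Strict loss | SAP-rule loss | Unchanged |
|---|---|---|---|
| 0.5 | Φ(−1.20) = 11.5% | Φ(−1.00) = 15.9% | 4.4% |
| 0.8 | Φ(−0.75) = 22.7% | Φ(−0.625) = 26.6% | 3.9% |

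The overstatement is about 4 percentage points. Over a wider assumed range (mean change 0 to 0.6 kg, SD 0.5 to 1.2 kg), simulation of rounded weights gives an unchanged share of about 3–8% with 0.1 kg readings and about 15–37% with 0.5 kg readings. Precision drives the size.

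**3. Effect on the comparison of arms.** Let the true loss rates be p1 > p0.

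- If the unchanged share t is equal in both arms, the difference is (p1 + t) − (p0 + t) = p1 − p0, so it does not move. The ratio (p1 + t)/(p0 + t) is smaller than p1/p0.
- If the shares differ, the difference moves by t1 − t0, in either direction.

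Example with 0.1 kg readings, SD 0.8 kg and assumed mean changes of +0.55 and +0.25 kg. The second arm has strict loss Φ(−0.375) = 35.4% and SAP-rule loss Φ(−0.25) = 40.1%.

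| Rule | Loss, +0.55 kg arm | Loss, +0.25 kg arm | Difference | Ratio |
|---|---|---|---|---|
| Strict | 22.7% | 35.4% | 12.7 points | 1.56 |
| SAP | 26.6% | 40.1% | 13.5 points | 1.51 |

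Here the ratio shrinks slightly and the absolute difference grows slightly.

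**4. Which outputs are affected.** The 8.6.3 gain/loss tables use the 6.3 categories directly. The 8.7 weight-loss table has no rule of its own, and 6.3 holds the only definition in the SAP, so carrying it over is the natural reading but still an inference. If it is carried over, a zero change counts as loss in the safety table, whereas the protocol's safety endpoint requires a negative change.

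**The case against.** The strongest reply is that this is a drafting slip with little consequence. The definitions sit under exploratory variables and the tables are descriptive. The primary and secondary endpoints, the success criterion and the interim analysis do not use them. Mean, median, minimum and maximum change in weight are reported at each visit whatever the tie rule, so a real loss of weight would still show there. Counting ties as loss cannot hide loss. A programmer may also notice when gain and loss exceed 100%. All of this stands and limits the importance of the point. None of it makes the percentages right.

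Three stronger readings are tempting, and the documents do not support them.

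- A reader might infer that the weight-loss safety rate is certainly overstated. Section 8.7 does not cite 6.3, and losing weight in its ordinary sense excludes no change, so the effect there is conditional.
- A reader might infer that the rule dilutes any real difference between arms. The working shows that with similar tie rates only the ratio is attenuated. The absolute difference stays the same if ties are equally common and can grow if they are not.
- A reader might assume whole-pound readings and so a very large effect. The SAP specifies weight in kilograms, and nothing in the documents indicates that pounds were recorded and converted.

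**Conclusion.** The overlap is certain and nothing elsewhere in the documents corrects it. As written, the gain and loss percentages in the 8.6.3 tables are each too high by the unchanged share. The same holds for the 8.7 safety table only if the 6.3 rule is used there. The figure of about 4 percentage points at Week 12 rests wholly on the assumed precision, growth and SD; coarser recording would make it larger. This is a definite but local error that leaves every hypothesis test and the continuous weight analysis untouched.

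**What to change.** In Section 6.3, define weight gain as post-Baseline weight strictly above Baseline and weight loss as strictly below, and add a no-change row so that the three categories sum to 100%. In Section 8.7, refer to that definition for the weight-loss table, and reconcile it with the protocol's endpoint, which asks for a negative change and adds a clinical qualifier that the SAP does not carry over. State the precision to which weight is recorded, since it determines how often ties occur.

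The cost is two changed symbols, one table row and a cross-reference. It needs no new data and has no effect on power or Type I error.
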